INVESTIGATORS: [name] MD, MBA; [name] MD; [name] MD; [name], BSN, RN, CCRC

Title: Prospective Hemodynamic and Pharmacokinetic Analysis of Oxymetazoline Absorption during Functional Endoscopic or Turbinate Reduction Surgery or Adenoidectomy.

Background and Significance:

Oxymetazoline is an α -adrenergic agonist that is commonly used as a topical sympathomimetic agent in over-the-counter decongestant sprays. Its vasoconstrictive action on the blood vessels defines its clinical utility as both a decongestant and a topical hemostatic agent(1). It is used extensively by otolaryngologists for functional endoscopic sinus surgery (FESS), turbinate surgery, and adenoidectomy to produce vasoconstriction. Riegler et al. compared cocaine 4%, phenylephrine 0.25%, and oxymetazoline 0.05% for nasal vasoconstriction in pediatric patients undergoing functional endoscopic sinus surgery (2), Children who were treated with oxymetazoline had less bleeding and improved visualization compared with the other two vasoconstrictors. Heart rate decreased, but blood pressure was unchanged during the first ten minutes after application. However, the authors did not determine the cumulative dose of oxymetazoline. Although there is generally limited vascular absorption, when administered in larger doses, uptake of oxymetazoline can lead to significant systemic hemodynamic effects, most commonly hypertension related to its action on the α -adrenergic receptors of the smooth muscle of the vasculature that results in vasoconstriction. Furthermore, when used in even larger doses in young children, oxymetazoline can activate central adrenergic receptors and lead to serious adverse effects including cardiovascular instability, respiratory depression, and neurologic complications, which may be potentially life-threatening (3-6) In the operating room, this reflex bradycardia may not always occur because general anesthetics, particularly volatile anesthetics, attenuate the baroreceptor response. Bradycardia may also be a consequence of the direct action of oxymetazoline on central α adrenergic receptors in the locus ceruleus and central vasomotor areas of the brainstem. Our institution recently reported a case of oxymetazoline induced postoperative hypertension in a three year old child following inferior turbinate reduction and adenoidectomy. (7)

Giannakopoulos studied the cardiovascular effects and pharmacokinetics of an intranasal 3 percent tetracaine/0.05 percent oxymetazoline spray at two different dose levels in adult dental patients. (8) A small decrease in heart rate and a small increase in diastolic blood pressure was noted. Serum levels of oxymetazoline were measured and a half-life of 1.72 to 2.32 hours was noted. No similar pharmacokinetic studies have been reported in children. Latham and Jardine reported oxymetazoline-induced hypertension in a 4-year-old child. (9) They also sought to investigate alterations in the amount of medication delivered based on the delivery method. There was up to a 75-fold increase in the volume of medication administered when the bottle was held inverted. Squeezing the bottle in the upright position resulted in a mist with the delivery of $28.9 \pm 6.8 \mu\text{l}$ of fluid. The amount delivered was effort independent. When the bottle was inverted and squeezed, the volume administered was effort dependent.

Current practice at NCH is to soak nasal pledgets with full strength oxymetazoline and insert a varying number of pledgets on the nasal turbinates or into the sinuses for hemostasis, or on the adenoid bed.

This proposed study will assess the hemodynamic effects and measure the systemic absorption of topically applied oxymetazoline in patients undergoing functional endoscopic sinus surgery, turbinate surgery, or adenoidectomy.

Specific Aims/Objectives:

The primary objective is to determine the perioperative hemodynamic effect of oxymetazoline applied topically for vasoconstriction in patients undergoing functional endoscopic sinus surgery, turbinate surgery or adenoidectomy using blood pressure and heart rate intraoperatively (OR) and postoperatively (PACU) until discharge from phase 1 of the PACU.

A secondary objective is to measure the plasma concentrations of oxymetazoline at discrete time periods from instillation and correlate with hemodynamic effects, as well as determine the rate of decline in levels as a function of time.

A secondary objective is to assess the degree of bleeding and ease hemostasis rated by a single observer to minimize variability.

Hypotheses:

Instilled oxymetazoline causes an increase in blood pressure in the intraoperative and postoperative period and, though absorption is rapid and variable, effects are related to serum level of oxymetazoline.

The decline in hemodynamic effect and serum levels is a function of time.

Hemostatic effect is determined by dose of oxymetazoline instilled by the surgeon.

Methods:

Thirty patients of [name] who will undergo functional endoscopic sinus surgery, turbinate surgery or adenoidectomy and are anticipated to receive oxymetazoline-soaked pledgets for hemostasis will be enrolled.

Patients ages 2 through 18 yrs. will be enrolled if they are scheduled for

- 1) Functional endoscopic sinus surgery (ten patients)
- 2) Turbinate reduction (with or without tonsillectomy and/or adenoidectomy) (ten patients)
- 3) Adenoidectomy (ten patients)

Patients will be excluded if they have been treated with oral decongestants or antihistamines within 24 hours of surgery, are taking anticoagulants, have a history of nasal trauma within past 3 months, have a history of epistaxis within past 3 months, have a history of hypertension or cardiac disease, or are allergic to oxymetazoline.

There will be no change in the conduct of the general anesthetic care related to the study protocol. Our usual practice will be followed. For premedication, midazolam (0.5 mg/kg to a maximum of 15 mg) will be administered 15-45 minutes prior to the procedure at the discretion of the attending anesthesiologist. An inhalation induction with sevoflurane or an intravenous induction with propofol will be performed by the attending anesthesiologist and titrated to attempt to maintain the bispectral index (BIS) between 40 and 60 to ensure adequate and similar depth of anesthesia. It will not be considered a protocol violation if the BIS is not maintained at this level. Fluid will be administered to

attempt a total of 15 ml/kg for procedures less than 1 hr or maintenance plus replacement for procedures greater than 1 hr. It will not be considered a protocol violation if this amount of fluid is not infused.

Blood pressure and heart rate and will be recorded at 5 min intervals until discharge from PACU or final blood draw, whichever comes first.

Blood samples will be drawn at approximately 5 (3-6 min), 10 (8-12 min), 20 (18-22 min), 45 (30-60 min), 90 (75-120 min) and 150 (135-240 min) minutes via a second IV, placed after the induction of anesthesia. Each sample will be collected in a 3 ml heparin green-top tube. The maximum volume per patient is 18 ml, which is 1.2 tablespoons of blood or approximately 1.5% of the total blood volume in a 2 yr old. This a fraction of the usual blood loss associated with sinus, turbinate, and adenoid surgery. If patient is ready to be discharged from PACU prior to the completion of blood sampling, the sampling will be discontinued and the second IV will be removed.

Plasma Samples

Collection

1. Collect blood sample to analyze oxymetazoline plasma concentrations using a 3 mL - draw green-top Vacutainer® Hemogard collection tube containing heparin.
2. Immediately following collection, gently invert blood sample 8-10 times to mix the anticoagulant in the tube with the blood and place on ice. Separate plasma using standard centrifugation procedures (centrifuge tube approximately 10-15 minutes at 2000g). If plasma has not completely separated, re-centrifuge the specimen for an additional 3-4 minutes. Transfer duplicate plasma aliquots of approximately equal volume. Samples will be stored immediately after plasma separation and may be kept in a dedicated refrigerator at $+5 \pm 2^{\circ}$ C.
3. A minimum of 250 μ L plasma will be required.

Processing

1. Transfer duplicate plasma aliquots of approximately equal volume, using standard laboratory technique, into two appropriately-labeled polypropylene tubes (A and B) with screw caps.
2. Labels should be secured to each storage tube using a strip of tape wrapped completely around the tube. Labels should contain the following information: Protocol and study numbers; subject number; study day and time of sample collection; aliquot (Aliquot A or Aliquot B); sample ID (as provided by Sponsor) and biological matrix to be analyzed (whole blood).

Storage

1. Store plasma aliquot A and plasma aliquot B samples in a GLP-compliant freezer at -70° C. Plasma should not be stored at room temperature at all and at $+5 \pm 2^{\circ}$ C for no longer than 24 hours.

Plasma aliquot B samples will remain stored at the Clinical Study Unit as a backup in a GLP-compliant freezer at -70° C, until shipment is requested.

The surgeon will place oxymetazoline-soaked pledgets according to usual practice. [name] will make two different observations to assess the amount of bleeding and ease of hemostasis (10)

- 1) A four point scale to record subjective bleeding following removal of pledgets

- 0= none, 1= minimal/restricted, 2=moderate/diffuse ooze, 3=severe/brisk
- 2) A six point scale to assess ease of hemostasis
1=very easy, 2=easy, 3=usual, 4=some effort required, 5=difficult, 6=extremely difficult

Blood pressure and heart rate and will be retrieved from EPIC for analysis

Prior to the study Drs. [name] & [name] determined that 10 pledgets in 15 ml of oxymetazoline (1.5 ml per pledget) provided the necessary amount of oxymetazoline for clinical use. The number of pledgets placed will be recorded at the time of insertion. If placement is separated by greater than five minutes, then this will be recorded as a separate event. The volume at each time point and the total dose will be recorded. Age-matched, procedure matched control patients not receiving oxymetazoline will be used for comparison. We will do a retrospective chart review of the control patients for hemodynamic parameters.

Statistical Analysis:

Compare the incidence of hypertension using systolic blood pressure and mean arterial pressure criteria using age adjusted normative tables

Compare the incidence of bradycardia defined as HR < 60 bpm, or tachycardia defined as HR>100

Compare the use of vasodilators for the treatment of hypertension

Compare the use of atropine/glycopyrrolate for the treatment of bradycardia

Compare the volume of oxymetazoline instillation and hemodynamic changes

Measure the serum level of oxymetazoline at approximately 5 (3-6 min), 10(8-12 min), 20(18-22 min), 45 (30-60 min), 90 (75-120 min) and 150 (135-240 min) minutes using the protocol specified above.

Compare the degree of bleeding and the ease of hemostasis using the subjective rating scale by the single surgeon observer.

All demographic and parametric data will be presented as mean (\pm SD). Normally distributed interval data will be analyzed using unpaired t-test. Nominal or ordinal data will be analyzed using Chi-squared contingency table or a Fisher's exact test with Yates correction factor. A $P < 0.05$ will be used to express statistical significance.

REFERENCES:

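### Matching controls on age and procedure alone leaves surgeon and calendar period inseparable from oxymetazoline in the comparison with untreated children

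*Combined protocol and SAP*

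**What the plan says.** The primary objective in Specific Aims/Objectives is hemodynamic: "The primary objective is to determine the perioperative hemodynamic effect of oxymetazoline applied topically for vasoconstriction". Hypotheses puts it causally, with oxymetazoline raising blood pressure during and after surgery.

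Methods takes the treated group from one clinician's practice, ten children for each of three procedure groups: "Thirty patients of [name] who will undergo functional endoscopic sinus surgery" and the other two operations. They are chosen by expected exposure, since those who "are anticipated to receive oxymetazoline-soaked pledgets for hemostasis will be enrolled". No randomisation is described. Statistical Analysis also points to one operator, with bleeding and hemostasis compared "using the subjective rating scale by the single surgeon observer".

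The unexposed group is described in two sentences near the end of Methods: "Age-matched, procedure matched control patients not receiving oxymetazoline will be used for comparison", and "We will do a retrospective chart review of the control patients for hemodynamic parameters". Neither these sentences nor any other part of the document gives a control surgeon, a calendar window, a number or ratio of controls, or the order in which controls are identified and their outcomes read.

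Background and Significance describes the site's habit: "Current practice at NCH is to soak nasal pledgets with full strength oxymetazoline", placed on the turbinates, in the sinuses or on the adenoid bed.

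Statistical Analysis names the unpaired t-test, chi-squared and Fisher's exact test. It plans no adjustment, stratification or matched analysis.

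**The concern.** Untreated children are the plan's only unexposed reference for hypertension, bradycardia, tachycardia and the use of drugs to treat them. These outcomes can also depend on surgical stimulation, length of operation, anesthetic and recovery-room practice, and charting. Any of these may differ between surgeons or between years.

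Treated children share one clinician and one enrolment period, while controls may not. A difference between the groups could then come from the drug, the surgeon or the period, and the planned tests cannot tell these apart. The bias could create an apparent effect or hide a real one.

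A second route to bias is selection. The charts are reviewed to obtain blood pressure and heart rate, and no rule requires the control list to be settled first. A choice among eligible charts made with those values in view could tilt the comparison either way, and this could not be undone later.

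**Working it through.** **Comparing the two groups as described**

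| Feature | Treated | Control |
|---|---|---|
| Source | One named clinician | Not stated |
| Period | Prospective | Retrospective, no window |
| Procedure | Three groups of ten | Matched |
| Age | 2 through 18 years | Matched, tolerance not stated |
| Exclusions | Listed in Methods | Not stated to apply |
| Number | 30 | Not stated |

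The matching handles age and procedure. Surgeon and period are handled by neither the matching nor the analysis.

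**The plan's own figure.** 10 + 10 + 10 = 30, which agrees with the stated total. It cannot be derived from a power calculation, because the plan gives no effect size, SD, event rate or power.

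**How far a shift could mislead (illustration).** The 30 treated children and the 0.05 level are from the document. The following are assumptions: 30 controls, a two-sided test, a true drug effect of zero, and a difference of d SDs between the groups due to surgeon or period.

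SE of the difference in means, in SD units = √(1/30 + 1/30) = 0.258.

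Probability of P<0.05 = Φ(d/0.258 − 1.96) + Φ(−d/0.258 − 1.96).

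| Assumed shift d | d/SE | Probability of P<0.05 |
|---|---|---|
| 0 | 0 | 5% |
| 0.2 | 0.77 | 12% |
| 0.3 | 1.16 | 21% |
| 0.5 | 1.94 | 49% |
| 0.8 | 3.10 | 87% |

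To put this in mmHg, an assumed SD of 10 mmHg makes the SE 10 × √(2/30) = 2.58 mmHg. A shift of 5 mmHg is then 5/2.58 = 1.94 SE, the 0.5 SD row.

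**Adding controls makes this worse.** At d = 0.5:
- With 60 controls, SE = √(1/30 + 1/60) = 0.224 and the probability is 61%.
- With 90 controls, SE = √(1/30 + 1/90) = 0.211 and the probability is 66%.

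The bias stays the same while the standard error falls.

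**Comparison with what the study can detect.** With 30 v 30, 80% power needs a difference of (1.96 + 0.84) × 0.258 = 0.72 SD. A shift of 0.5 SD is about 70% of that (0.5/0.72).

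**Incidence of hypertension.** This is the first comparison listed in Statistical Analysis. Summing exact binomial probabilities over all 30 v 30 tables in which Fisher's test gives P<0.05:
- 10% v 10%: 0.9%
- 10% v 20%: 9.6%
- 10% v 30%: 37%

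The rates are assumed. Fisher's test is conservative at this size, so the binary comparison is less easily misled than the mean, but it is not protected.

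**The case against.** The strongest reply is that the problem is allowed by silence and has not been shown to occur. Three stronger readings are tempting, and the document supports none of them.

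- A reader might infer that surgeon and period are in fact confounded with the drug. No section says that controls come from other surgeons or earlier years.
- A reader might infer from the site's practice that untreated charts will mostly come from other surgeons or earlier years. The practice is described for the whole site, so other current surgeons may be users too. Enrolling only children expected to receive pledgets suggests that some of the same clinician's patients may not. No frequency of use is given. Same-surgeon, same-period controls may be scarce, but they are not ruled out.
- A reader might infer that controls will be picked with outcomes already seen. The text fits equally well with identifying controls first and abstracting afterwards. The order is simply not specified.

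Some features do help. Age and procedure matching removes real differences, hypertension is judged against age-adjusted tables, and blood pressure and heart rate are retrieved from the electronic record. Anesthesia follows usual practice with a bispectral index target, but that target is not binding ("It will not be considered a protocol violation if the BIS is not maintained at this level"), and nothing shows that it applied to controls. None of these features addresses surgeon or period.

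Two points of reading also stand. That there is one surgeon rests on a removed name in the singular and on the single-observer wording. The listed comparisons do not name their groups. That treated versus control is meant follows from the stated purpose of the controls and the primary objective.

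**Conclusion.** The concern holds as a statement about what the plan can and cannot separate. As written, a surgeon or period difference cannot be told apart from an oxymetazoline effect in the only comparison with untreated children, and selection of controls with outcomes in view is not prevented. Whether either bias will occur, and in which direction, cannot be known from the document.

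Its size cannot be estimated either. The percentages above are a scale, resting on assumed shifts, assumed event rates and an assumed 30 controls. No single row should be quoted as the expected error rate.

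The analyses of instilled volume, plasma level and decline over time lie within treated children and do not depend on the controls. They have no untreated reference, so they cannot replace the comparison.

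The change should be made before control data are collected.

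**What to change.** 1. Build the control list from age, procedure, surgery date, surgeon and non-receipt of oxymetazoline only. Fix it before any control blood pressure or heart rate is abstracted.
2. State the number of controls per treated child. Match on procedure, then age, preferring the same surgeon where such controls exist, then the nearest surgery date within a prespecified window. State in advance how the window widens if too few controls are found.
3. Apply to controls those trial exclusions that can be read from charts.
4. Record surgeon, surgery date and operative duration for both groups.
5. Replace the unpaired tests for this comparison with an analysis that respects the matching, for example a paired or matched-set model for means and conditional logistic regression for incidence. Add a sensitivity analysis adjusted for period.
6. Describe the result as an association. If few or no same-surgeon controls exist, say that the surgeon effect remains inseparable. Adjustment cannot recover it when all treated children belong to one surgeon.

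The cost is a selection rule in the protocol and two or three extra chart fields. Some matches may be less close in age, or there may be fewer controls, especially for functional endoscopic sinus surgery. Treatment, enrolment and blood sampling do not change.

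### The decongestant exclusion names only oral products, so a child who used an oxymetazoline nasal spray that day can be enrolled and the carry-over can be neither seen nor subtracted

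*Combined protocol and SAP*

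**What the plan says.** The exclusion paragraph in Methods reads: "Patients will be excluded if they have been treated with oral decongestants or antihistamines within 24 hours of surgery". The remaining exclusions are anticoagulants, recent nasal trauma, recent epistaxis, and children who "have a history of hypertension or cardiac disease, or are allergic to oxymetazoline". None concerns nasal or topical decongestants.

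Background and Significance describes oxymetazoline as "commonly used as a topical sympathomimetic agent in over-the-counter decongestant sprays".

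On sampling, Methods say: "Blood samples will be drawn at approximately 5 (3-6 min), 10 (8-12 min), 20 (18-22 min), 45 (30-60 min"), with further samples at about 90 and 150 minutes. No sample before placement is listed. The dose record covers the number of pledgets, the volume at each placement and the total. Prior spray use is not mentioned, either for the enrolled children or for the retrospective controls.

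Specific Aims/Objectives time the plasma levels from instillation and ask for their rate of decline. Statistical Analysis relates instilled volume to hemodynamic change. Hypotheses tie the hemostatic effect to the dose that the surgeon instills.

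**The concern.** The plan screens out oral decongestants but not prior intranasal use of the drug it sets out to measure. The enrolled children are having sinus, turbinate or adenoid surgery, so home use of such a spray is plausible, although the documents give no frequency.

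The volume and hemostasis analyses, and the reading of plasma levels as time from instillation, treat the pledgets as the only source of drug. If a child arrives with drug on board:

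- The measured levels are not purely a function of time since instillation, and the fitted decline mixes two exposures.
- The recorded volume understates total exposure in the volume-effect and hemostasis comparisons. This is noise if home use is unrelated to the number of pledgets placed, and bias if it is related.
- A control who used a spray at home is not truly unexposed.

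Each surgical group has ten children, so one affected child is 10% of a group (1/10).

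**Working it through.** The plan states no figure for carry-over, so there is none to reproduce. The check sizes it from the plan's own inputs.

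**Inputs, all from Background and Significance except the last**

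- Half-life: "Serum levels of oxymetazoline were measured and a half-life of 1.72 to 2.32 hours was noted". This comes from adult dental patients given a tetracaine/oxymetazoline spray. The plan says that no similar study exists in children.
- Upright squeeze: "Squeezing the bottle in the upright position resulted in a mist with the delivery of" 28.9 ± 6.8 microlitres.
- Inverted bottle: "There was up to a 75-fold increase in the volume of medication administered when the bottle was held inverted". The volume is described as effort dependent.
- Pledget, from Methods: "10 pledgets in 15 ml of oxymetazoline (1.5 ml per pledget").

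**Assumptions**

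- Decay is first-order.
- The spray and the pledget solution have the same strength and the same fractional absorption.
- The 75-fold figure multiplies 28.9 microlitres, which the plan does not say explicitly.

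**Volumes relative to one pledget**

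- Upright: 0.0289 / 1.5 = 1.93%.
- Inverted, maximum: 75 × 0.0289 = 2.17 ml, and 2.17 / 1.5 = 144.5%.

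**Fraction remaining** = 0.5^(t / half-life). The amount left, as a percentage of one pledget's volume, is the relative volume times that fraction. Ranges run from a half-life of 1.72 h to one of 2.32 h.

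| Hours since home use | Fraction remaining | One upright squeeze | One maximal inverted squeeze |
|---|---|---|---|
| 2 | 44.7–55.0% | 0.9–1.1% | 65–80% |
| 4 | 20.0–30.3% | 0.4–0.6% | 29–44% |
| 8 | 4.0–9.2% | 0.1–0.2% | 6–13% |
| 24 | 0.01–0.08% | under 0.01% | 0.01–0.11% |

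The last two columns scale with the number of squeezes and inversely with the number of pledgets. For two pledgets (3.0 ml) and use 4 h earlier:

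- Four upright sprays: 4 × 0.0289 / 3.0 = 3.85%, times 0.200 to 0.303, leaves 0.8 to 1.2%.
- Two maximal inverted squeezes: 4.335 / 3.0 = 144.5%, times the same fractions, leaves 29 to 44%.

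These percentages are relative to the whole pledget volume. At the 3–6 minute sample the share would be larger if pledget drug is still being absorbed.

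**Rate of decline.** If both sources were fully absorbed and decayed with one common half-life, their sum would decay with it too, and the slope would be unaffected. The distortion arises while pledget drug is still being absorbed, or if its early decline is faster than that of the older residue. The 150-minute sampling target spans only about 1.1 to 1.5 half-lives (2.5 / 2.32 and 2.5 / 1.72), so these early phases can make up much of what is observed.

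**The case against.** The strongest reply is that ordinary use leaves little. Upright sprays a few hours earlier leave about 1% of the pledget volume, and the plan does not say that home users invert the bottle. The 75-fold figure is a maximum, and a remaining fraction of 45–55% describes what may be a very small dose. All of this stands: it limits the expected size but leaves the eligibility gap open.

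Three stronger readings are tempting, and the documents do not support them.

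- A reader might infer that the concentration-effect relation is biased. Residual drug is part of the measured level, and the hypothesis relates effects to serum level whatever its source. Home use does not by itself distort that relation.
- A reader might infer that a pre-placement blood pressure baseline is shifted. The plan defines no such baseline. Hypertension is judged against age-adjusted norms and heart rate against fixed cut-offs. The Background also describes absorption as generally limited and reports only small changes after the adult nasal spray.
- A reader might infer that volume-effect and hemostasis results are biased in a known direction. The documents show no link between home use and pledget number, and give no duration for local vasoconstriction. Noise is the default expectation.

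It can also be said that recording home use would keep children whom exclusion would lose. That is a fair alternative, but the plan provides for neither.

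**Conclusion.** The gap in the wording is certain: same-day intranasal use of the study drug is permitted, and nothing later in the plan would reveal it. What is exposed is the set of levels timed from instillation, their apparent rate of decline, and the volume-effect and hemostasis comparisons.

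The size is uncertain. One squeeze 2 to 4 h before placement leaves about 0.4–1.1% of one pledget's volume if the bottle was upright, and about 29–80% at the inverted maximum. These figures rest on an adult half-life, equal strength and absorption, and the reading of the 75-fold multiple given above. The proportion of children affected is not stated. It would be wrong to conclude that carry-over is usually large or that the results as a whole are invalid. The amendment is nonetheless worth making, because the rule admits unmeasured exposure to the very drug being assayed.

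**What to change.** Reword the criterion to exclude *oral or intranasal/topical decongestants (including oxymetazoline) or antihistamines*, keeping the existing 24-hour window. On the adult half-life, less than 0.1% of an earlier level remains at 24 h. The investigators should confirm that the window is adequate for children aged 2 to 18.

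Add an explicit question on nasal spray use at screening, since the plan describes none. Apply the same check to the chart-review controls where the chart allows, and report how many charts are silent.

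If the investigators prefer not to exclude, the alternative is to record the product and time of any use and add a plasma sample before placement, so that carry-over is visible.

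The cost is a short eligibility amendment and one screening question, with a few otherwise eligible children not enrolled. The alternative keeps those children but adds a blood draw.

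### The plan does not show that the retrospective controls had anesthetic care comparable to the treated children, and names no data with which to check or adjust for it

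*Combined protocol and SAP*

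**What the plan says.** The primary objective (Specific Aims/Objectives) is the effect of topical oxymetazoline on blood pressure and heart rate in the operating room and in phase 1 recovery.

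**Anesthetic care (Methods).** The paragraph opens "There will be no change in the conduct of the general anesthetic care related to the study protocol" and says that usual practice applies. Induction is with sevoflurane or propofol, and midazolam is at the anesthesiologist's discretion. Anesthesia is "titrated to attempt to maintain the bispectral index (BIS) between 40 and 60 to ensure adequate and similar depth of anesthesia", but "It will not be considered a protocol violation if the BIS is not maintained at this level". For fluid, staff are to "attempt a total of 15 ml/kg for procedures less than 1 hr or maintenance plus replacement for procedures greater than 1 hr", and again "It will not be considered a protocol violation if this amount of fluid is not infused".

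**Controls (end of Methods).** They are patients who did not receive oxymetazoline, matched on age and procedure. Of their data the protocol says: "We will do a retrospective chart review of the control patients for hemodynamic parameters". Their number, period, site and eligibility criteria are not given. The same section says that blood pressure and heart rate will be taken from EPIC.

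**Analysis (Statistical Analysis).** The list compares rates of hypertension, bradycardia and tachycardia, and use of vasodilators and of atropine or glycopyrrolate. The tests are the unpaired t-test for normally distributed interval data and chi-squared or Fisher tests for nominal or ordinal data. No covariate is named.

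**The concern.** The comparison with controls is not randomized, so the groups are comparable only as far as matching, restriction or adjustment makes them so. The protocol itself treats anesthesia as relevant to the outcome: it wants depth to be similar, and the Background says that "general anesthetics, particularly volatile anesthetics, attenuate the baroreceptor response" when it discusses reflex bradycardia. Yet no anesthetic variable is matched on, named for extraction or adjusted for.

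At stake is how the primary result is read. A difference in blood pressure or heart rate could be due to oxymetazoline, to anesthetic or fluid differences, or to both. Equally, a real drug effect could be masked. With the data the plan names, a reader could not tell which.

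**Working it through.** The plan states no power calculation, effect size or SD, so there is no figure to reproduce. The check has two parts.

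**1. What is controlled, measured and adjusted for**

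| Factor | Treated | Controls | Matched on? | Named for extraction? | Adjusted for? |
|---|---|---|---|---|---|
| Age, procedure | three procedures, 10 children each | matched | yes | implied by the matching | no |
| Induction agent | sevoflurane or propofol | not stated | no | no | no |
| Midazolam | discretionary | not stated | no | no | no |
| Depth | BIS 40-60 attempted, not binding | not stated | no | no | no |
| Fluid | target attempted, not binding | not stated | no | no | no |
| Rescue drugs | compared | compared, by implication | no | implied by the analysis list | not applicable (outcome) |

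The rescue-drug comparisons imply that some medication data will come from the control charts. Those drugs are responses to a hemodynamic event. They do not describe the anesthetic that the child was receiving when it occurred.

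**2. What an unadjusted background difference would do (illustration only)**

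Inputs:
- Treated group: 30 (Methods).
- Controls: not stated; 30 and 60 assumed.
- Level: 0.05 (Statistical Analysis); two-sided assumed.
- True oxymetazoline effect: none, assumed.
- Shift in mean blood pressure from anesthetic differences: d = 0, 0.25, 0.50 and 0.75 SD. All are assumed; the documents support none of them in particular.

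The probability of P<0.05 comes from the noncentral t distribution with n1 + n2 − 2 degrees of freedom and noncentrality d / √(1/n1 + 1/n2).

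- 30 against 30, d = 0.50: 0.50 / √(1/30 + 1/30) = 0.50 / 0.258 = 1.94 on 58 degrees of freedom, giving 47.8%.
- 30 against 60, d = 0.50: 0.50 / √(1/30 + 1/60) = 0.50 / 0.224 = 2.24 on 88 degrees of freedom, giving 59.9%.

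| Shift d (SD) | 30 vs 30 | 30 vs 60 |
|---|---|---|
| 0 | 5% | 5% |
| 0.25 | 15.9% | 19.8% |
| 0.50 | 47.8% | 59.9% |
| 0.75 | 81.5% | 91.3% |

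More controls do not help: they make a biased difference more likely to be significant. At d = 0 the rate is the nominal 5%, so the problem is a systematic difference between the groups and not ordinary chance variation.

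The table applies to a t-test on mean blood pressure. It does not quantify the listed comparisons of hypertension, bradycardia and tachycardia rates, which would use chi-squared or Fisher tests, although the same bias can affect them.

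**The case against.** The strongest reply is that the protocol calls this anesthetic care unchanged usual practice, with non-binding targets. If the controls came from the same practice, they may have been managed in the same way. This stands as far as it goes. A reader might infer that the treated children had guided anesthesia and the controls unguided anesthesia; the documents do not support that, because they do not say how the controls were managed. But the reply does not show that care was comparable either, since the control period, site and eligibility are not given, and usual practice as described leaves agent, midazolam, depth and fluid open.

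A reader might also infer that a blood pressure rise managed by deepening the anesthetic is lost to the analysis. That does not follow. Pressures are recorded every 5 minutes, and a charted high reading counts toward the hypertension rate however it was treated. Only the separate count of vasodilator use would miss it.

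Nor do the documents show that the anesthetic data do not exist or cannot be obtained. They show only that the plan does not name them.

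Finally, the illustrative percentages would apply to any t-test with a shifted mean, and nothing ties a given d to agent, depth or fluid in this trial. That is correct. They show sensitivity and do not estimate bias.

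**Conclusion.** The point holds in a limited form. Comparability of anesthetic care between treated children and chart-review controls is not shown, and with the data and tests that the plan names an imbalance could be neither detected nor adjusted for. It could inflate or hide an oxymetazoline effect on the primary measures.

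The size and direction are unknown from the documents. The illustrated range, about 16% to 82% false-positive results with 30 per group, rests on the assumed control number, the assumed shifts of 0.25 to 0.75 SD, a two-sided test and no drug effect. The conclusion does not depend on these figures. It rests on what the Methods and Statistical Analysis leave out. The change is a cheap improvement that should be made.

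**What to change.** Change the control and EPIC text in Methods, and Statistical Analysis, as follows.

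1. State the source, period and number of the controls.
2. In both groups, extract anesthetic agent, midazolam premedication, fluid in ml/kg, and depth (BIS or agent concentration) where charted.
3. Report the balance of these variables between the groups.
4. Keep the unadjusted blood pressure and heart rate comparison. Add one that respects the matching and adjusts for a small pre-specified set, for example agent, premedication and fluid given before instillation. Restricting fluid to that period avoids adjusting for a response to the drug.
5. Controls have no instillation time, so define a procedural time point that serves as its equivalent.
6. State in advance that BIS will be used descriptively if it is often missing.

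The cost is a few more fields in an extraction that is already planned, and some analysis wording. Thirty treated children, 10 per procedure, can support only a few covariates, so the adjusted result will be imprecise and unmeasured differences will remain. Anesthetic care itself does not change.
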